4.0 Study Endpoints

[figure not shown]
4.1 The primary study endpoint is the enrollment of 10 participants per study arm (normal weight/active, normal weight/sedentary, overweight, obese/active, and overweight, obese/sedentary).

4.2 There are no safety endpoints for this study.

5.0 Study Intervention/Investigational Agent

N/A – no intervention/investigational agent

6.0 Procedures Involved

- 6.1 This is a cross-sectional study design (see above figure). The study team aims to assign N=10 participants to each arm of the study (normal weight/active, normal weight/sedentary, overweight, obese/active, and overweight, obese/sedentary).
- 6.2 Participants who fall into the overweight/obese category (~20) will also be recruited for the AAAA2 – Exercise study (AAAA2 study with an intervention and post intervention tests), which includes the same testing as AAAA2. The AAAA2 - Exercise study will only include those with a BMI percentile from the 85th to 99th percentile. It also has an exercise intervention (same as the BATE study), which 50% of study participants will be randomly assigned to. All 3 visits (measurement session 1, measurement session 2 and insulin sensitivity visit) will be completed before and after the exercise intervention. For those participants that complete testing in the AAAA2 study and are interested in the AAAA2 – Exercise study, their AAAA2 data will be used as baseline data in the AAAA2 - Exercise study. They will then consent for the AAAA2 - Exercise study and start their exercise intervention, or wait until their follow-up visits.

Orientation Session: 1 hour. The orientation session will serve as a visit to explain the details of the study, with example images of what tests will be completed. P/A/C documentation will also be completed at this visit if they decide to participate. If a participant and parent opt for in-person orientation, after consent, their height, weight and blood pressure will be collected to classify each participant into an arm of the study. If a virtual orientation is chosen, height and weight will be reported from them, according to their most recent measures. Following P/A/C for both in-person and virtual orientation, the **Contact Information Questionnaire** will be completed. After completion of the orientation session, the parent and subject will be instructed to complete the **Medical History and Demographics Questionnaire** prior to the first measurement session visit. This questionnaire will be sent through a RedCap link.

Measurement Session 1: 5.0-6.0 hours. This study visit will take place at the Don Chisholm Center in the morning (<9:00am) following an overnight dietary fast. This study visit will be conducted to assess appetite control and relevant variables under laboratory conditions. The measures conducted in this visit are provided below

- **Surveys**
 - **TFEQ**
 - **CEQ**
 - **VAS Pre-Meal**
 - **VAS Post-Hedonic**
 - **VAS**
- **Anthropometry and Body Composition via DXA.**
 - Fat mass (FM) and fat-free mass (FFM) will be measured using a whole-body dual energy X-ray absorptiometer (DXA, Lunar DPX system, version 3.6).
- **Waist and Hip Measurements.** Waist measured in centimeters, two inches above the umbilicus at skin level, at the end of a normal breath expiration, with arms relaxed at sides. Hip measured in centimeters at the maximum circumference of the buttocks, with arms relaxed at the sides.

- **Fixed/*Ad libitum* Meals.** Appetite (see below) will be assessed following a fixed standard breakfast (40% of RMR, composed of 55% carbohydrate, 15% protein, 30% fat). Food intake (total kcals) will also be assessed using an *ad libitum* meal served three hours after the fixed meal. Participants will be instructed to eat until comfortably full and informed that they can request more of the meal at any point.
- Each plate of food will be weighed before and after serving, without the subjects' knowledge.
- **Appetite and Eating Behavior** Subjective assessment of hunger and palatability will be completed using self-rated visual analogue scales (VAS) [51], with each scale consisting of a 10-cm long line separating statements such as "not at all hungry" and "extremely hungry". [VAS tools are widely used to assess health conditions and show good test-retest reliability [52], especially in within-subject repeated measures study designs [53].] Perceptions of dietary restraint, disinhibition, and hunger will be measured during each measurement session using the Three Factor Eating Questionnaire (TFEQ) [54]. The Control of Eating Questionnaire (CEQ) will be used to assess hunger, fullness, cravings, the desire to eat certain types of foods, and the ability to resist urges to eat [55]. Objective assessment of appetite will be completed using blood samples taken from an indwelling catheter, and analyzed for episodic regulation of the following fasting and satiety hormones: glucose, insulin, leptin, ghrelin, glucagon-like peptide 1 (GLP-1), and peptide YY (PYY). All samples will be mixed a standard preservative (400 μ L of 10,000 KIU aprotinin), centrifuged, the plasma divided and stored in -80°C freezer until later analysis.
- **Resting Metabolic Rate.** Resting metabolic rate (RMR) will be measured via indirect calorimetry using a ventilated hood and open-circuit system metabolic cart (ParvoMedics, Salt Lake City, Utah) following a standard protocol [56].
- Thermic effect of feeding (TEF) will measure the energy expenditure resulting from digestion following the fixed meal using the ventilated hood.

Continuous, Free-living Home Assessments of Energy intake/expenditure: 7 days between Measurement Session 1 and Measurement Session 2.

- The free-living assessment period is defined as the 7 days between Measurement Session 1 and Measurement Session 2. During these 7 days, subjects will be completing two energy intake/ expenditure assessments while going about everyday life activities at home. These assessments are explained in proceeding bullets.
- Energy intake will be assessed during the free-living 7-day assessment period via standardized 24-hour dietary recalls. Energy intake will be assessed using three dietary recalls occurring on randomly selected non-consecutive days over each 7-day free-living assessment period

(including at least one weekend day) to minimize preparation that could bias recall, by a team of experienced staff employing a multi-pass approach, which utilizes prompts to reduce food omissions and standardizes the interview methodology.

- Physical activity and energy expenditure will be estimated using two physical activity monitors (Actigraph GT9X Link, Actigraph Inc., and ActivPAL, PAL Technologies), which assesses movement using tri-axial accelerometry. The monitors themselves are not being studied as a part of this protocol, and while they do not have 501(k) documents, the devices used in this study are not considered to be more than minimal risk.

Measurement Session 2: 2.0 hours. This study visit will take place at the Don Chisholm Center. This visit will include a DXA scan, mitochondrial function testing via NIRS, and cardiorespiratory fitness testing (CRF):

- **Body Composition via DXA:**
 - Fat mass (FM) and fat-free mass (FFM) will be measured using a whole-body dual energy X-ray absorptiometer (iDXA, Lunar DPX system) with the participant dressed in surgical scrubs and in bare feet.
- **Grip Strength Testing:**
 - Grip strength will be assessed using a handheld dynamometer. The participant will hold the device in one hand in line with the forearm at the level of the thigh, away from the body.
 - The participant squeezes the handgrip dynamometer as hard as possible without holding their breath. Neither the hand nor the dynamometer should touch the body. The test is repeated twice in each hand and scored as the sum of the highest measurement from each hand.
- **Mitochondrial Function via Near-Infrared Spectroscopy**
 - Assessment of skeletal muscle oxidative capacity using near-infrared spectroscopy (NIRS) will be performed. The specific protocol used to measure skeletal muscle oxidative capacity was initially described by Ryan et al (2014). An ISS Medical (Champaign IL, USA) Dual-Channel OxiplexTS advanced NIRS device that uses Frequency Domain technology to provide an absolute determination of oxy[heme] and deoxy[heme] in various tissues will be used. This device uses 8 near infrared lasers emitting 690nm to 830nm wavelengths which penetrate the skin without damage and are reflected to a Hamamatsu R928 detector. The instrument is controlled through a laptop computer and specialized software package (both provided by ISS Medical).
 - The NIRS muscle probe will be positioned on the skin longitudinally above the belly of the vastus lateralis muscle of the right leg, halfway between the patella and the hip. The probe will be secured using double-sided adhesive tape and Velcro straps around the thigh. After device calibration and a 30-minute warm-up period, blood pressure cuff designed for the thigh (specific size will be dependent on the patient) will be placed proximal to the NIRS probe as high as anatomically possible. The inflation of the cuff will be

- controlled with a rapid-inflation system set to a pressure between >200mmHg, powered with a 15-gallon air compressor.
- Participants will perform short duration (10-15 second) voluntary isometric contractions of the quadriceps to increase muscle oxygen consumption. Following voluntary contraction, recovery kinetics of the muscle will be measured using a series 10 transient arterial occlusions with timing of 5 seconds on – 5 seconds off; followed by a series of another 10 transient arterial occlusions with timing of 10 seconds on – 10 seconds off. Post each occlusion, the rate of change (slope) in the decline in deoxy[heme] will be calculated. The resting procedure will be performed twice with results averaged.
- **Thigh Circumference and Skinfold Measurement**
 - To identify optimal NIRS probe placement, mid-thigh circumference will be measured using the right thigh at the midpoint between the inguinal crease and the proximal border of the patella.
 - Skin and adipose tissue thickness will be measured at the site of the NIRS probe using skinfold calipers. The technician will ‘pinch’ the skin and adipose tissue with their thumb and fore finger and measure the tissue thickness with a set of calipers.
- **Cardiorespiratory Fitness Testing:**
 - Submaximal oxygen consumption (fitness test) and maximal oxygen consumption will be assessed using an indirect calorimetry system with mouthpiece via standard protocols using a treadmill. Prior to the start of the test, resting blood pressure, heart rate, and oxygen saturation will be assessed using an automated vital signs monitor.
 - The submaximal exercise test will consist of walking at two speeds for five minutes each estimated as ‘light’ and ‘moderate’ intensity by the research technician. Following a five-minute break, the maximal test will be performed using the Bruce protocol. The Bruce protocol is the most widely used fitness testing protocol used in the US and consists of a series of three-minute stages that gradually increase the speed and grade of the treadmill. The majority of individuals reach volitional fatigue 9-12 minutes into the test. During both the submaximal and maximal tests, heart rate will be measured via monitor (Polar) and gas exchanged will be measured using indirect calorimetry (TrueOne, ParvoMedics, Parvo, UT, USA). Following completion of the test, blood pressure, heart rate, and oxygen saturation will be assessed using an automated vital signs monitor to ensure an appropriate post-exercise response.
- **Muscular Strength Testing:**
 - Muscular strength will be assessed with a one-repetition maximum (1-RM) test for the chest press and seated leg press using weight stack equipment (Paramount, St. Louis, MO, USA) following the protocol used by Co-I [name] [57, 58]. Resistance will be progressively increased by 2.5-20 kg until a maximal lift is achieved with a full range of motion within four attempts (3-5 min rest between trials). Muscular strength will be calculated

as the sum of the 1-RM scores for the bench and leg press per kg of body weight.

Insulin Sensitivity Visit: 5 hours. This study visit will take place at University of Kansas Medical Center Clinical and Translational Science Unit (KUMC CTSU) located on the Fairway campus. This visit will involve baseline blood samples and blood samples taken throughout the insulin sensitivity test.

- **Hyperinsulinemic euglycemic clamp.**

- The hyperinsulinemic-euglycemic clamp is the gold standard for assessing insulin sensitivity as stated by the World Health Organization. It allows the insulin levels to be 'clamped' at a constant state so that insulin stimulated by physiological measures can be assessed. Insulin sensitivity can be determined by the amount of glucose that is infused to maintain euglycemia. The higher the amount of glucose that needs to be infused while insulin is clamped, the more insulin sensitive the subject is.
- The hyperinsulinemic euglycemic clamp will be performed at the University of Kansas Medical Center Clinical and Translational Science Unit (KUMC CTSU), located at [name]. The CTSU contains 17 clinic rooms, 2 cognitive testing rooms, and open workspaces for up to 5 visiting study coordinators. The CTSU's infusion center has 11 infusion bays supported by two nursing stations and activity in the center has steadily grown. The center also supports research infusions and intensive and complex metabolic research assessments such as hyperinsulinemic-euglycemic clamps (see Morris et al. 2016). There is a CTSU medical monitor available for Adverse Events. The CTSU medical monitor is contacted when there is an urgent, medical concern / AE with the participant; The medical monitors are MD's or NP's / APRN's (aka Advanced Practice Registered Nurse). NOTE: This is in addition to the study-specific DSMB.
- Participants will arrive fasted (12-hours overnight), and one catheter will be inserted into an antecubital vein of one arm to infuse insulin and 20% dextrose, and another catheter will be inserted into a contralateral vein in the hand/arm for blood sampling. The participant will rest quietly and we will collect 3 baseline blood samples to establish baseline glucose levels. If baseline values are <60 mg/dL the procedure will not continue. Once baseline assessments have been completed, a primed continuous infusion of regular human insulin plus albumin will be administered at a rate of $40 \text{ mU} \cdot \text{m}^2 \text{ body surface area}^{-1} \cdot \text{min}^{-1}$ along with a variable infusion of 20% dextrose to

maintain euglycemia to match baseline levels (expected 90-100 mg/dL). Blood glucose measurements will be completed every 5 minutes for determination of glucose infusion rate using a Nova Statstrip handheld glucometer and YSI analyzer as needed.

- After approximately 90 minutes of acclimatization, a 30-minute data collection period will occur. Insulin sensitivity will be determined as average glucose concentration and glucose infusion rate during this 30-minute period of euglycemia (defined as glucose concentration and glucose infusion rate coefficient of variation <10%).
- After this 30-min period, A 60-minute recovery period begins. Insulin infusion is stopped, and glucose infusion continues at the last rate for 30-min to prevent hypoglycemia. Glucose infusion is stopped 30 minutes into recovery if blood glucose levels remain at acceptable levels.
- Participants will be provided a full lunch meal (e.g., sandwich, potato chips, drink) following the cessation of insulin infusion to minimize the chances of hypoglycemia. Participants will be provided with a 20 mEq potassium pill to take with food. In rare instances hypokalemia can occur resulting from hyperinsulinemia and increased glucose disposal. Potassium supplementation helps prevent this from occurring.
- Following the cessation of glucose, all participants will remain under observation at the CTSU for the final 30 minutes of recovery to monitor for hypoglycemia.
- Participants can be released if participant is asymptomatic and blood glucose levels are acceptable at the end of the observation period.
- Blood is drawn from a hand/arm vein after the hand/arm has been placed under an electric blanket and this technique is called arterialization, as it makes the blood in the vein have similar characteristics to that flowing in the artery by dilating the vessels in the arm. This is a well-accepted technique that allows us to avoid performing an arterial IV placement. The hand/arm will be placed under the blanket for the entire testing procedure.
- Insulin Mixing Procedures: The CTSU Investigational Pharmacy (located onsite) will store the insulin and albumin. The unused insulin and albumin will be returned to the pharmacy after each study. CTSU nurses will mix the insulin, albumin, and saline. For the mixing procedures, 2 mL of human albumin is injected into a bag of 250 mL sterile saline and gently inverted to mix the solution. Using an insulin syringe, 1.25 mL of insulin is added to the albumin/saline mixture and gently inverted to mix the solution.
- The mixing of insulin with albumin is essential to minimize the binding of insulin to the saline bag, as well as the catheter tubing. This procedure for mixing the infusate was described in the initial

report of the hyperinsulinemic-euglycemic technique (DeFronzo et al, 1979) using blood rather than albumin and is still utilized by labs that perform the hyperinsulinemic-euglycemic clamp. We are using albumin in this study to prevent the possibility of clotting associated with the use of blood.

6.3 Data collected during the study includes self-report survey data (see myIRB local documents) as well as DXA, RMR, VO₂, TEF, NIRS, and blood test results. Anthropometric measurements such as height and weight will also be collected. Dietary recall data and activity monitor data will be collected during the free-living assessment period (sample output available on local documents). Finally, insulin sensitivity will be determined through the Hyperinsulinemic-Euglycemic Clamp procedure.

6.4 There are no plans for long-term follow-up beyond study completion.

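### The NIRS slope rule names a decline in deoxy[heme] after each occlusion; muscle oxygen consumption shows as a rise during the occlusion, so the rule as written does not give oxidative capacity

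*Combined protocol and SAP*

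**What the plan says.** The relevant text is in section 6.0, Measurement Session 2, under the heading on mitochondrial function by near-infrared spectroscopy.

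- Purpose: "Assessment of skeletal muscle oxidative capacity using near-infrared spectroscopy (NIRS) will be performed".
- Stimulus: short "voluntary isometric contractions of the quadriceps to increase muscle oxygen consumption".
- Sampling: "recovery kinetics of the muscle will be measured using a series 10 transient arterial occlusions", with "timing of 5 seconds on – 5 seconds off", and then "another 10 transient arterial occlusions with timing of 10 seconds on – 10 seconds off".
- Cuff: a "rapid-inflation system set to a pressure between >200mmHg".
- Calculation: "Post each occlusion, the rate of change (slope) in the decline in deoxy[heme] will be calculated".

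The calculation sentence is the only rule for turning the traces into numbers. The section defines no slope during the cuff-inflated seconds, no recovery curve and no rate constant. It says that the device determines both oxy[heme] and deoxy[heme] in absolute terms. It attributes the method to a 2014 protocol, which has no entry in the reference list (section 30.0). The resting procedure is run twice and averaged; no averaging rule is given for the recovery series.

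**The concern.** The section wants the time course of muscle oxygen consumption after a contraction. With arterial inflow stopped, consumption can be read directly, because oxygen use converts oxy[heme] to deoxy[heme] in blood that is not being replaced. Consumption is therefore the rise in deoxy[heme], or equally the fall in oxy[heme], while the cuff is inflated. The written rule has the opposite direction and the other phase. A decline in deoxy[heme] after an occlusion is what happens when the cuff opens and fresh blood arrives.

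At stake is whether the reported NIRS value means what its label says. An analyst who follows the sentence would extract up to 20 slopes per recovery test, each depending on perfusion, and would have no stated way to turn them into an index of oxidative capacity.

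**Working it through.** The documents give no figure to reproduce, so the check is on the logic of the rule, followed by a simulation.

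**From the protocol.** First series: 10 × (5 + 5) s = 100 s. Second series: 10 × (10 + 10) s = 200 s. Together that is 20 occlusions over 300 s. The cuff is set above 200 mmHg, so inflow is taken as zero while it is inflated.

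**Mass balance.** Let D be deoxy[heme] above its arterial level, V(t) oxygen consumption and Q(t) perfusion:

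dD/dt = V(t) − Q(t)·D(t), with Q = 0 while the cuff is inflated.

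- Cuff inflated: slope = V(t). It is positive and free of perfusion.
- Cuff released: slope = V(t) − Q(t)·D(t). It is negative only when the inflow term exceeds consumption, and it depends on perfusion, which the protocol does not plan to measure.

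**Assumed values, not from the documents.** V(t) = 0.1 + 0.9·exp(−k·t), with true k of 0.015, 0.025 or 0.035 per s; D starting at V(0)/Q(0); and five perfusion patterns, either constant or decaying exponentially. Blood-volume shifts are ignored. Units of D are arbitrary.

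**Hand check, first occlusion, k = 0.025.** Rise over 5 s = 0.1 × 5 + (0.9/0.025) × (1 − exp(−0.125)) = 0.50 + 4.23 = 4.73, so the occlusion slope is 4.73/5 = 0.946 whatever the perfusion. At release V = 0.1 + 0.9 × exp(−0.125) = 0.894.

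- Perfusion constant at 0.1: D = 1/0.1 + 4.73 = 14.73, and the slope is 0.894 − 0.1 × 14.73 = −0.58.
- Perfusion falling from 0.5 towards 0.05 at rate 0.01: D = 1/0.5 + 4.73 = 6.73, Q = 0.05 + 0.45 × exp(−0.05) = 0.478, and the slope is 0.894 − 0.478 × 6.73 = −2.32.

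Consumption is identical in the two cases, yet the slopes at release differ fourfold. Averaged over the first 3 s after release, the simulation gives −0.53 and −1.20.

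**All 20 occlusions.** A mono-exponential was fitted to the slopes during occlusion, and separately to the decline slopes over the first 3 s after release. Occlusion-phase slopes returned 0.0150, 0.0250 and 0.0350 per s in all 15 scenarios. Post-release slopes gave these rate constants (per s):

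| Perfusion pattern (per s) | true 0.015 | true 0.025 | true 0.035 |
|---|---|---|---|
| constant 0.1 | 0.0007 | 0.0067 | 0.0110 |
| 0.2 to 0.05, rate 0.01 | 0.0070 | 0.0137 | 0.0192 |
| 0.2 to 0.05, rate 0.03 | 0.0046 | 0.0128 | 0.0190 |
| 0.5 to 0.05, rate 0.01 | 0.0135 | 0.0229 | 0.0314 |
| 0.5 to 0.05, rate 0.03 | 0.0233 | 0.0293 | 0.0362 |

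The columns overlap: a fitted value near 0.023 arises from a true 0.015 and from a true 0.025. Within any one row the fitted value does increase with the true one, so the slope carries some information on consumption, but it cannot be read without knowing perfusion.

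The move from 5 s to 10 s occlusions also changes the size of the post-release decline, but it is not the whole explanation. Fitted to the ten 5 s occlusions alone, a true 0.025 came out anywhere from 0.0000 to 0.0277.

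**The case against.** The strongest reply is that this is a slip of the pen. Everything around the sentence describes the occlusion method, and a specific 2014 protocol is named as its source. If deoxy was typed for oxy, and the opening words mean only that slopes are computed afterwards, the intended rule is the fall in oxy[heme] during occlusion, which is sound. That is plausible, and it stands as a reason not to assume that the analysts will compute a reperfusion slope. It does not rescue the text: reading the opening words as a matter of timing still leaves a decline in deoxy[heme], which does not occur while inflow is blocked. Since the cited protocol is missing from the reference list, the sentence is the only rule these documents give.

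A second reply is that the reference to recovery kinetics already implies a curve fit. It does imply one, but neither the fit nor its summary parameter is stated. This gap is secondary to the wrong slope.

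A third is that nothing planned depends on the result. This is largely right. Section 2.2 defines metabolic function by the clamp and calorimetry, section 4.0 has only an enrolment endpoint, and section 19.1 adds insulin sensitivity alone to the models. NIRS appears as a Session 2 test and among the data collected (section 6.3). One qualification is section 6.2: AAAA2 results become baseline data in the Exercise study, which repeats the same visits.

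Three stronger readings may tempt a reader, and the documents do not support them:

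- That oxidative capacity is lost. The device measures both signals, so occlusion-phase slopes can still be extracted.
- That the written slope is a pure blood-flow index. The mass balance shows a mixture of consumption and flow.
- That differences in flow between activity or weight groups would be reported as mitochondrial differences. No group comparison of NIRS is planned, and no figure for such a flow difference is given.

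**Conclusion.** The rule is wrong as written. Its direction and phase do not match the quantity that the section sets out to measure, and applied literally it would not give the recovery of muscle oxygen consumption. Confidence in this is high, because it follows from stopped inflow and from the sign of the change, not from any assumed value. The numerical spread, such as 0.0067 to 0.0293 per s for a true 0.025, rests on the assumed consumption and perfusion patterns and shows only that the error can be large.

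The reach is small. The hypotheses, the endpoint and the SAP models are untouched; the exposure is to one additional measure and to its use as baseline in the Exercise study. Any effect on reported results is uncertain, since the sentence may not be what the analysts intend to do.

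**What to change.** Before any NIRS analysis, replace the calculation sentence with wording such as:

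> During each occlusion (cuff inflated), the slope of the rise in deoxy[heme] (or fall in oxy[heme]) will be calculated, and the post-contraction slopes will be fitted against time with a mono-exponential to give the recovery rate constant as the index of oxidative capacity.

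Then reconcile this wording with the 2014 protocol: which signal is used, whether a blood-volume correction is applied, and the form of the fit. Add that protocol to the reference list. The documents mention no blood-volume correction and no averaging of the recovery series, so neither should be added unless the cited method calls for it. Use the same corrected rule for the Exercise study, so that baseline and follow-up are derived alike.

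The cost is protocol wording and signal processing. No new procedure or participant time is needed, provided that the traces are kept for the cuff-inflated seconds as well as after release.
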